Study Protocol

The use of buffered soluble alendronate 70 mg (Steovess/Binosto) after denosumab discontinuation to prevent increase in bone turnover.

Sponsor/Chief Investigator

Ghent University Hospital,

[name]. [name], Dept. Of Rheumatology

Principal Investigator:

[name], PhD, Dept. Of Rheumatology – Ghent University Hospital

Sub-Investigators:

[name], PhD Dept. of Rheumatology - Ghent University Hospital

EudraCT number: 2019-003570-11

Protocolnumber: BC-6072

August 09 2019 – Version 1.0

Protocol Signature Page

Principal/Chief Investigator signature

I confirm that I have read and understood protocol version 1.0 dd. 09 August 2019. I agree to comply with the study protocol, the principals of GCP, research governance, clinical trial regulations and appropriate reporting requirements.

Signature..... Date.....

Print name

Protocol synopsis

Study Type	Investigator Sponsored Study				
Funder	Amgen and EffRx Pharmaceuticals				
Study Design	This is a randomized study to investigate the effect of weekly 70mg effervescent alendronate [Steovess 70mg/weekly] on bone turnover after denosumab [Prolia 60 mg Q3M] discontinuation in patients with erosive osteoarthritis of the interphalangeal finger joints.				
Study Design	At the earliest three months but no later than four months after the last denosumab injection, 40 subjects will be randomized to effervescent alendronate administered for either 24 (n=20) or 48 weeks (n=20).				
Investigational Therapy Subjects will be randomized to receive open label effervescent alendronate (Steovess/Binosto) for 24 or 48 weeks. All subjects will receive Calcium/v supplementation.					
Efficacy Objectives	The primary objective of this study is to investigate if weekly intake of 70mg effervescent alendronate can prevent increases in bone turnover above the premenopausal reference range at week 48 and if there is difference between using alendronate for 24 or 48 weeks, started three months after the last injection of denosumab. Other objectives of the study are:				
	 to explore the impact on dual-energy X-ray absorptiometry (DEXA) parameters after 24 and 48 weeks of treatment 				
	- to assess radiographic changes and investigate if new erosive joints develop at week 24 and 48				
Main Endpoints	 The primary endpoint of this objective is to assess the number of patients that maintain C-terminal telopeptide of type I collagen (CTx-I) levels within the premenopausal reference range at 48 weeks. Secondary endpoints are the assessment of the number of patients that maintain CTx-I levels within the premenopausal reference range at week 12 and 24 as well as the changes in CTx-I and N-terminal propeptide of type I procollagen (P1NP) levels from baseline until 12, 24 and 48 weeks after randomization to effervescent alendronate. Co-exploratory objectives are changes in T-score at lumbar spine and hip from baseline to week 24 and week 48, and the radiographic changes at the finger joints in terms of new erosive joints and GUSS change between W24 and W48 and baseline. 				
Hypothesis	The main hypothesis is that effervescent alendronate will be able to maintain bone turnover markers within the pre-menopausal reference range, thereby reducing the likelihood of bone turnover associated changes.				
Study Sites	1 site – the UZ Ghent site				
Subjects	40 subjects for the alendronate follow-up study				
Enrolment	72 weeks				
Main Eligibility Criteria	Subject must have completed our three year study 'RANKL-blockade for the treatment of erosive osteoarthritis (OA) of interphalangeal finger joints' (EudraCT number: 2015-003223-53; Protocolnumber: AGO/2015/008)				
Study treatment Duration	48 weeks				

Table of Contents

- Protocol Title and Investigators
- Protocol signature page
- Protocol synopsis

1. Background and Rationale

- 1.1 Disease background
- 1.2 Denosumab
- 1.3 Effervescent alendronate
- 1.4 Rationale for study design
- 1.5 Hypotheses

2. Study Objectives and Endpoints

3. Experimental Plan

- 3.1 Study design and schematic
- 3.2 Number of sites
- 3.3 Number of subjects
- 3.4 Estimated study duration
- 3.5 Subject Eligibility
 - 3.5.1 Inclusion criteria
 - 3.5.2 Exclusion criteria
- 3.6 Criteria for withdrawal

4. Medication

- 4.1 Composition and dosing
- 4.2 Producer
- 4.3 Distributor
- 4.4 Packaging
- 4.5 Administration way
- 4.6 Labelling:
- 4.7 Storage conditions:
- 4.8 Known side effects of the medication
- 4.9 Drug accountability

5. Procedures

- 5.1 Study procedures
- 5.2 Study table
- 5.3 Sample processing

6. Randomisation

7. Reporting requirements for investigational product complaints

- 8. Concomitant therapy
- 9. End of study
- 10. Adverse Events/Adverse Event reporting
 - 10.1. Definitions

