1.2 Denosumab

Denosumab (Amgen), is a fully human monoclonal antibody designed to inhibit RANKL (RANK Ligand). RANKL binds to RANK, which exists as a cell surface receptor molecule on "pre"-osteoclasts: precursors of osteoclasts.

Binding of RANKL to RANK acts as the primary signal for bone removal in normal physiological bone remodeling and in a number of pathological conditions, e.g. malignant tumors and bone metastasis.

Activation of RANK by RANKL promotes the maturation of pre-osteoclasts into osteoclasts. Denosumab inhibits osteoclasts' maturation, function and survival by binding to and inhibiting

August 09 2019 – Version 1.0

RANKL. This mimics the natural action of osteoprotegerin, an endogenous RANKL inhibitor that presents with decreasing concentrations in patients who are suffering from osteoporosis. This protects bone from degradation, and helps to counter the progression of the disease.

Denosumab was approved by the EMA for use in postmenopausal women with osteoporosis at increased risk for fracture at the dose of 60 mg sc every 6 months (Prolia), and for the prevention of skeletal-related events in patients with bone metastasis from solid tumors at the dose of 120 mg every 4 weeks (XGEVA).

More recently, denosumab was shown to retard the progression of structural lesions in rheumatoid arthritis, an unapproved indication for the drug.^{5,6} Its dosing and safety profile depended on the different medical conditions in which the drug was used. Patients with osteoporosis and rheumatoid arthritis received 60 mg and up to 180 mg injected SC, every 6 months, respectively.

Experience from clinical studies indicates that side effects depend on the dosage.

According to Prolia Summary of Product Characteristics (SmPC)⁷, pain in extremities and musculoskeletal pain (including back pain and joint pain) were among the most common adverse reactions.

In patients treated for osteoporosis a rare unwanted effect included low calcium levels, especially when in case of an impaired kidney function. Patients must therefore be adequately supplemented with calcium and vitamin D levels before starting and during denosumab therapy. In the postmarketing setting, rare cases of severe symptomatic hypocalcaemia have been reported. Clinical monitoring of calcium level is recommended before each dose and, in patients predisposed to hypocalcaemia, within two weeks after the initial dose.

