1.5 Hypotheses

It is hypothesized that effervescent alendronate will be able to maintain bone turnover markers within the pre-menopausal reference range thereby reducing the likelihood of bone turnover associated changes, after discontinuation of Prolia treatment in a non-osteoporotic population.

2. Study Objectives and Endpoints

The objectives of the effervescent alendronate treatment after denosumab discontinuation are to investigate if weekly intake of effervescent alendronate can prevent increases in bone turnover above the premenopausal reference range^{*} at week 48 and if there is difference between using alendronate for 24 or 48 weeks, started at the earliest three months but no later than four months after the last injection of denosumab.

Other objectives of the study are:

- to assess the changes in bone turnover after 12 and 24 weeks,
- to explore the impact on dual-energy X-ray absorptiometry (DEXA) parameters after 24 and 48 weeks of treatment
- to assess radiographic changes and investigate if new erosive joints develop at week 24 and 48

The primary endpoint of this objective is the number of patients that maintain C-terminal telopeptide of type I collagen (CTx-I) within the premenopausal reference range at 48 weeks.

Secondary endpoints are the number of patients that maintain CTx-I within the premenopausal reference range at week 12 and 24 as well as the changes in CTx-I and N-terminal propeptide of type I procollagen (P1NP) from baseline until 12, 24 and 48 weeks after randomization to effervescent alendronate.

Co-exploratory objectives are changes in T-score at lumbar spine and hip from baseline to week 24 and week 48, and related to the underlying erosive hand OA disease, the radiographic changes at the finger joints in terms of new (radiographic) erosive joints (n) and GUSS change (Δ) between W24 and W48 and baseline.

Safety-objective

This study will assess the safety of the weekly administration of effervescent alendronate 70mg in the population of patients with erosive OA. Safety evaluations will be made by recording the incidence of AE/SAE

^{*} Reference range: CTX-I (IVD kit) Non menopausal women < 700ng/l. Menopausal women < 730ng/l. Adult male >20 to 120 years: < 695ng/L; P1NP (IVD kit): Male > 45 years: 12.8-71.9 µg/L Non menopausal women: 13.7-71.1 µg/L Menopausal women: < $82.6 \mu g/L$

3. Experimental Plan

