3.1 Study design and schematic

This is a randomized study to investigate the effect of effervescent alendronate on BTM after denosumab discontinuation.

At the earliest three months but no later than four months after the last denosumab injection, 40 subjects will be randomized to effervescent alendronate administered for either 24 (n=20) or 48 weeks (n=20). The randomization code will be generated by a randomization manager. Randomization will be done in blocks of four.

Study schematic

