4.1. Composition and dosing

After denosumab discontinuation subjects will be randomized to receive open label effervescent alendronate (Steovess) for 24 or 48 weeks. Effervescent alendronate a bisphosphonate as effervescent tablets that should be taken once a week. Each effervescent tablet contains 70 mg alendronic acid as 91.37 mg of alendronate sodium trihydrate. Excipients are sodium dihydrogen citrate, citric acid anhydrous, sodium hydrogen carbonate, sodium carbonate anhydrous, strawberry flavour [Maltodextrin (Maize), arabic gum, propylene glycol (E 1520), nature-identical flavouringsubstances], acesulfame potassium and sucralose. Each tablet contains 602.54 mg of sodium. Effervescent alendronate is supplied as a white to off-white round effervescent tablets of 25 mm diameter, flat faced with bevelled edges.

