## 2.2 Hypothesis and objectives

It is hypothesized that effervescent alendronate will be able to maintain bone turnover markers within the reference range thereby reducing the likelihood of bone turnover associated changes, after discontinuation of denosumab treatment in a non-osteoporotic population.

The **primary objective** of this study is to assess the effect of effervescent alendronate after denosumab discontinuation on the change in bone turnover markers after 48 weeks in a non-osteoporotic population and to assess if there is a difference between using oral alendronate after 24 or 48 weeks.

The **secondary objective** is to evaluate the effect of effervescent alendronate after denosumab discontinuation on bone mineral density in this non-osteoporotic population and assess difference in oral alendronate therapy for 24 versus 48 weeks.

**Exploratory objectives** are to study the effect of oral alendronate therapy after denosumab discontinuation on erosive destructive progression at the subchondral bone in erosive hand OA patients and to assess the effect of oral alendronate on their hand pain scores.

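### The primary objective asks whether alendronate prevents a rise in bone turnover, but with no never-treated group or benchmark the design can only estimate continuing versus stopping at week 24

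*Protocol*

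**What the plan says.** The primary objective has two halves. The first, in the protocol synopsis and section 2, is whether "weekly intake of 70mg effervescent alendronate can prevent increases in bone turnover above the premenopausal reference range at week 48". The second is whether 24 and 48 weeks of alendronate differ. SAP section 2.2 keeps both: it sets out "to assess the effect of effervescent alendronate after denosumab discontinuation on the change in bone turnover markers after 48 weeks" and then the comparison of durations. SAP section 4.1 still describes the aim as finding out whether alendronate is able to maintain the markers.

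On design, protocol section 4.1 says "subjects will be randomized to receive open label effervescent alendronate (Steovess) for 24 or 48 weeks", with 20 patients planned per arm (section 3.1). Treatment starts "At the earliest three months but no later than four months after the last denosumab injection".

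The primary endpoints differ. Protocol section 2 uses the number of patients with CTx-I in range at week 48. SAP section 4.1 uses the between-arm difference in CTX-I and PINP after 48 weeks. Under SAP sections 4.2 and 5.3 the in-range counts are secondary, and the arms are compared by Fisher's exact test.

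Earlier visits also count. In protocol section 2, "Secondary endpoints are the number of patients that maintain CTx-I within the premenopausal reference range at week 12 and 24", and SAP section 4.2 lists weeks 12, 24 and 48.

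**The concern.** Prevention is a causal claim: fewer patients go out of range than would have done without the drug. To support it, the plan needs patients who never received alendronate, or a justified figure for what would have happened to them. It has neither. Protocol section 1.1 says only that increases are expected once patients leave the denosumab study, without giving size, timing or the proportion expected to cross the limit.

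If the plan is followed as written, a high in-range count answers the first half of the primary objective by default. The same count could arise because alendronate worked, or because few of these non-osteoporotic patients would have crossed the upper limit anyway. The plan offers no way to tell these apart.

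**Working it through.** There is no stated power or sample-size figure to reproduce; protocol section 11.3 says none was calculated. The check covers what each visit can identify, how far a count without a comparator can be read, and the week-12 timing.

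**1. What each visit can identify**

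| Visit | 24-week arm | 48-week arm | Randomised contrast in alendronate |
|---|---|---|---|
| Week 12 | on drug | on drug | none |
| Week 24 | completing 24 weeks | completing 24 weeks | none |
| Week 48 | scheduled off since week 24 | on drug | continuing versus stopping |

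Only week 48 carries a randomised contrast. It concerns the second 24 weeks of alendronate, not alendronate versus nothing.

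**2. Reading a count without a comparator (illustrative counts)**

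Up to week 24 the arms are treated alike, so pooling is natural there. Suppose 32 of 40 are in range (80%). The exact 95% limits are the 2.5% quantile of Beta(x, n−x+1) and the 97.5% quantile of Beta(x+1, n−x). With x = 32 and n = 40 they are 64% and 91%.

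The probability of at least 32 of 40, if p0 is the in-range rate without alendronate, is the sum over k = 32 to 40 of C(40,k) p0^k (1−p0)^(40−k):

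| Assumed p0 | P(at least 32 of 40) |
|---|---|
| 60% | 0.006 |
| 70% | 0.11 |
| 80% | 0.59 |
| 90% | 0.98 |

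The same result is strong evidence of an effect at p0 = 60% and none at p0 = 80%. The documents do not give p0.

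For one arm at week 48, 18 of 20 in range would have exact 95% limits of 68% and 99%. Again there is no value to compare them with.

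**3. The between-arm comparison of counts**

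Exact power of the two-sided Fisher test at 0.05 with 20 per arm, under assumed week-48 in-range rates (continued versus stopped), is 24% for 90% versus 70%, 49% for 90% versus 60%, 74% for 90% versus 50%, and 91% for 90% versus 40%. A non-significant difference could therefore mean a lasting benefit from 24 weeks, no rebound above the limit, or too few patients. It would not show prevention.

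**4. Side note: timing of week 12**

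One month is 365.25/12/7 = 4.348 weeks, so 3 months is 13.04 weeks, 4 months is 17.39 and 6 months is 26.1. The visit window is ±7 days (protocol section 5.2).

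- Earliest week-12 sample: 13.04 + 11 = 24.0 weeks after the last injection.
- Latest: 17.39 + 13 = 30.4 weeks.
- Week 48, nominal: 13.04 + 48 = 61.0 to 17.39 + 48 = 65.4 weeks, or 14.0 to 15.0 months.

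Protocol section 1.2 describes the approved osteoporosis use as for women "at increased risk for fracture at the dose of 60 mg sc every 6 months (Prolia". Week 12 therefore straddles the end of one approved interval, and week 48 is 61.0 − 26.1 = 34.9 to 65.4 − 26.1 = 39.3 weeks beyond it. The CTx-I range in section 2 has only an upper limit (695 to 730 ng/L by sex and menopausal status), so a marker still suppressed by denosumab counts as in range.

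**The case against.** Four replies deserve weight.

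*The duration comparison is already in the objective, and the SAP makes it primary.* This is correct. The 24-week arm is scheduled off drug from week 24, so the week-48 between-arm difference, in markers or in counts, is randomised and can be credited to continued alendronate. A reader might infer that no in-range result can be credited to alendronate; the documents do not support that. What remains is the first half of the objective, the aim as worded in SAP 4.1, and the protocol's count as primary endpoint.

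*Rebound after denosumab is established, so staying in range is informative.* Protocol section 1.1 does cite a rebound, which makes an effect plausible. For this population it says only that increases are expected. The endpoint is also not any rise but crossing an upper limit, so a patient can rebound and still count as maintained.

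*The week-12 argument does not touch a week-48 objective.* Agreed; it bears only on secondary endpoints. A reader might also infer that success at week 12 is nearly guaranteed. The documents do not support this: section 1.2 gives an approved dosing interval, not how long CTx-I stays suppressed, and these patients received denosumab every 3 months. Patients starting at 4 months are sampled 28.4 to 30.4 weeks after the last injection, already past the interval.

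*A confidence interval still says something.* It does. It would be wrong to say that every untreated rate inside the interval fits equally well: 18 of 20 has probability 190 × 0.9^18 × 0.1^2 = 0.285 at a rate of 90% and 190 × 0.7^18 × 0.3^2 = 0.028 at 70%. The interval describes the in-range rate on treatment. It is silent on the rate without it.

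**Conclusion.** The concern holds for the words prevent, maintain and effect of alendronate when they rest on absolute in-range counts at any visit. This follows from the design and needs no assumed rate: no patient is never treated, and no benchmark or threshold is given. The figures above only illustrate how far the reading moves with an unknown rate, from 0.006 to 0.59 as the assumed untreated rate goes from 60% to 80%.

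It does not extend to the week-48 comparison of arms, which is a valid randomised estimate of continuing versus stopping at week 24. At week 48 the difficulty with the absolute count is the missing comparator, not denosumab carry-over. At week 12, residual denosumab is a possible further explanation; its extent is unknown because the documents do not give the duration of suppression. Week 24 shares the missing-comparator problem with week 12, so there is no reason to keep prevention statements at one and drop them at the other.

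The matter should be corrected because it governs what the primary objective may claim, and wording is enough to do so.

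**What to change.** 1. In the protocol synopsis and section 2, and in SAP sections 2.2 and 4.1, state the primary question as continuing versus stopping alendronate at week 24, read at week 48.
2. Reconcile the primary endpoint, which is an in-range CTx-I count in the protocol and a between-arm difference in CTX-I and PINP in the SAP, so that both documents name the same one.
3. Report in-range counts by arm at weeks 12, 24 and 48 descriptively with exact 95% confidence intervals, without calling them prevention or an effect of alendronate.
4. Add a sentence on week 12: both arms are on the same treatment, the sample falls 24.0 to 30.4 weeks after the last denosumab injection, the CTx-I range has no lower limit, and the counts may reflect residual denosumab.

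The cost is a narrower claim. No patients, visits or data are added, and treatment is unchanged.

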1.1 Disease background

Prolia (denosumab, anti-RANK ligand therapy) discontinuation is associated with a rebound in bone turnover and loss of bone mineral density (BMD).¹ These changes resulted in increases of fracture incidence in patients with postmenopausal osteoporosis back to background levels, however no excess in fracture incidence was observed.² Amongst the patients that presented with vertebral fractures after treatment discontinuation, there was a slightly higher incidence of multiple vertebral fractures in patients discontinuing Prolia versus those that discontinued placebo.³

In our study 'RANKL-blockade for the treatment of erosive hand osteoarthritis (OA) of interphalangeal finger joints' (EudraCT number: 2015-003223-53; Protocolnumber: AGO/2015/008) patients are randomized to placebo or denosumab (60 mg/Q3M) for 1 year followed by a two-year open label extension in which all subjects receive denosumab (60 mg/Q3M). Also in this non-osteoporotic population, increases in bone turnover are expected as soon as patients end study participation.

It is currently recommended that other anti-resorptive therapy may be warranted after Prolia discontinuation. One study describes the use of oral alendronate after denosumab therapy to maintain bone mineral density.⁴ However, gastro-intestinal upset and tolerability, as well as difficulty swallowing pills may limit oral alendronate use. In the current study proposal we want to examine the use of effervescent alendronate (Steovess/Binosto) in subjects that completed our hand erosive osteoarthritis study and therefore discontinued denosumab 60 mg/Q3M.We hypothesize that Steovess/Binosto will be able to maintain bone turnover markers within the pre-menopausal reference range thereby reducing the likelihood of bone turnover associated changes.

In erosive hand OA, destructive erosive changes, followed by remodelling is key characteristic for the disease. As in inflammatory rheumatic diseases, the RANKL pathway appears to be involved in the pathogenesis and hence, a therapeutic role of its blockade has been studied in the study described above. It is unknown if a potential rebound effect in bone turnover might also be associated with a rebound in erosive destructive progression at the subchondral bone.

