3.5 Subject eligibility

3.5.1 Inclusion criteria

A subject will be eligible for study participation if he/she meets the following criteria:

- Subjects must have completed the 48 weeks of the randomised placebo-controlled study phase followed by the 96 weeks open label denosumab 60 mg SC every 3 months phase. (EudraCT number: 2015-003223-53)
- Last denosumab injection less than four months ago
- Able and willing to give written informed consent and to comply with the requirements of the study protocol

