5.3 Sample processing

Blood samples collected during the visits will be used for clinical analysis.

At baseline visit, W12, W24 and W48 three extra serum tubes will be collected. After centrifugation (4000 RT/10min) the serum will be allocated in vials of 1ml and stored at -80°C. At the end of the study those samples will be send to an external lab for analysis of the BTM.

6. Randomisation

The randomization code will be generated by a randomization manager. Randomization will be done in blocks of four.

7. Reporting requirements for investigational product complaints

The following could be considered potential product complaints that need to be reported to EffRx Pharmaceuticals. The Investigator will email the product complaint reports to [contact] and [contact]. Should any such concerns or irregularities occur, the IMP will not be used until confirms that it is permissible to use was received.

Examples of Product Complaints:

- Packaging: for example, broken container or cracked container
- Usage: for example, subject or healthcare provider cannot appropriately use the product
- Labeling: for example, missing labels, illegible labels, incorrect labels, and/or suspect labels
- Change in IMP appearance: for example color change or presence of foreign material
- Unexpected quantity in bottle: for example number of tablets or amount of fluid
- Evidence of tampering or stolen material

8. Concomitant therapy

In patients treated for osteoporosis symptomatic hypocalcemia has occurred, generally in association with predisposing conditions. Therefore, patients must be adequately supplemented with calcium and vitamin D levels during Steovess therapy. A calcium (1000 mg) and vitamin D (880 IU) supplement will be provided during the study visits as of the baseline visit. Daily intake following the approved dosage and regimen is requested. This supplement is considered to be an auxiliary medicinal products. Relabeling is not requested.

9. End of study

End of study is 30 days after the last visit at week 48 of last patient.

10.Adverse Events/Adverse Event reporting

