#### 2.3 Study design

This is a monocentric randomized study to investigate the effect of effervescent alendronate on bone turnover markers after denosumab discontinuation. At the earliest three months but no later than

four months after the last denosumab injection, 40 subjects will be randomized to effervescent alendronate administered for either 24 (n=20) or 48 weeks (n=20). The randomization was performed by a randomization manager. The total treatment duration per subject is 48 weeks.

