### 5.2 Primary outcome analysis

The primary outcome analysis will be performed in an intention to treat approach, where drop-outs were considered as non-responders. Changes in bone turnover marker levels will be analysed with a linear mixed model. Data from all available time points will be used. Normal distribution will be checked and data transformations will be performed if necessary if assumptions of normality aren't reached. P-values and estimated marginal means will be calculated at different time points.

All analyses will be performed with a two-sided p-value. A p-value below 0.05 (p<0.05) will be considered statistically significant.

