#### 5.3 Secondary outcome analysis

Bone density measures will be analysed in an intention to treat approach, using a linear mixed model. Data from all available time points will be used. Normal distribution will be checked and data transformations will be performed if necessary if assumptions of normality are not reached. P-values and estimated marginal means will be calculated at different time points.

In addition, percentage changes in BMD and the percentage of patients with a BMD loss higher than the least significant change (LSC), which represents the smallest difference between successive measurements of BMD that can be considered a real change, will calculated. Here no intention to treat approach will be used.

The number of patients exceeding reference ranges will be calculated with an intention to treat approach, where drop-outs will be considered as non-responders. A Fisher's exact test was used to assess differences in patient numbers exceeding reference ranges between both treatment groups.

All statistical tests were two-tailed and a p-value below 0.05 ( $\alpha$ ) was considered statistically significant.

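### Entrants bring nominally 96 or 144 weeks of denosumab from the parent trial, and this known factor is neither a stratification factor nor a named model term; including it would buy modest precision.

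*Protocol*

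**What the plan says.** Protocol 1.1 describes the parent trial: "patients are randomized to placebo or denosumab (60 mg/Q3M) for 1 year followed by a two-year open label extension", with denosumab for all in the extension. Protocol 3.5.1, repeated in SAP 3.1.1, requires that subjects have "completed the 48 weeks of the randomised placebo-controlled study phase followed by the 96 weeks open label denosumab" treatment. Neither parent arm is excluded.

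On allocation, Protocol 3.1 and section 6 give 40 subjects, 20 per arm, and "Randomization will be done in blocks of four". SAP 2.3 adds only that "The randomization was performed by a randomization manager". No stratification factor is named.

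On analysis, SAP 5.2 states: "Changes in bone turnover marker levels will be analysed with a linear mixed model", using all available time points. SAP 5.3 and 5.4 plan the same kind of model for bone density and hand pain. None of the three lists its fixed effects. For the reference-range counts, SAP 5.3 says: "A Fisher's exact test was used to assess differences in patient numbers exceeding reference ranges between both treatment groups". SAP 5.1 plans a baseline summary of demographic and disease-specific characteristics and does not mention previous denosumab. Parent-trial arm does not appear as a covariate, subgroup or sensitivity analysis.

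**The concern.** The trial studies what follows the end of denosumab, and its entrants fall into two groups that differ in how long they took it. The split was created by an earlier randomisation, is fixed before this one, and is already held by the same sponsor. Adjusting for such a factor cannot introduce post-randomisation bias.

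Two things are at stake. First, with 20 per arm the two durations may be unevenly spread, and any effect of exposure on the markers then moves the 24 v 48 week contrast in that particular sample. Protocol 11.3 caps the sample at those leaving the extension phase who are willing to take part, so lost precision cannot be bought back by recruiting. Second, the trial also asks whether alendronate keeps markers in range at all. That question has no randomised control, and the proportion in range may depend on the mix of exposure histories. Without a breakdown the reader cannot tell.

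**Working it through.** The plan gives no power, SD or target difference, so there is no stated figure to reproduce.

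**Exposure (Protocol 1.1, 3.5.1).** Ex-placebo: 0 + 96 = 96 weeks. Ex-denosumab: 48 + 96 = 144 weeks. Ratio 144/96 = 1.5. These are nominal phase lengths, not doses received.

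**Chance imbalance.** The mix of parent arms among the 40 is not given. Let K be the number ex-placebo. The number of them in one arm of 20 is hypergeometric: P(k) = C(K, k) × C(40 − K, 20 − k) / C(40, 20). Summing the tails gives the probability that the arms differ by at least the stated number of ex-placebo subjects:

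| K (assumed) | 4 or more | 6 or more | 8 or more |
|---|---|---|---|
| 20 | 34.3% | 11.3% | 2.6% |
| 15 or 25 | 19.1% | 4.8% | 0.8% |
| 10 or 30 | 27.3% | 6.5% | 0.8% |

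For K = 20, a difference of 4 is 12 v 8 and a difference of 6 is 13 v 7. Simulating blocks of four gives the same figures to within simulation error, so blocking does not help.

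**Shift given an imbalance.** Let d be the exposure effect in within-group SD units. The documents give none, so d = 0.3 to 0.8 is assumed. For 12 v 8, shift = (12/20 − 8/20) × d = 0.2d, which is 0.06 to 0.16 SD. The standard error of the arm difference is √(2/20) = 0.32 SD. The shift is therefore 0.06/0.32 = 0.19 to 0.16/0.32 = 0.5 standard errors.

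For 13 v 7 the shift is 0.3d. With d = 0.25, 0.5 or 0.8, the false-positive rate conditional on that split is about 5.6%, 7.5% or 10.9%.

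**Precision.** With K = 20, the share of variance due to exposure is (d²/4)/(1 + d²/4): 2.2%, 5.9% and 13.8% for d = 0.3, 0.5 and 0.8. For a true arm effect of 0.8 SD (assumed), power with adjustment is about 72%. Without it, power is 71%, 69%, 65% or 62% for d = 0.25, 0.5, 0.8 or 1.0.

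**Which model term adjusts.** Suppose baseline is one of the modelled visits and the contrast is arm by week 48. A main effect of parent arm takes the same value at every visit, so it cancels from each subject's change and leaves that contrast as it was. Simulated complete data (40 subjects, four visits, random intercept, 12 v 8 split, post-baseline exposure effect of 0.8 SD) confirm this: the estimate and its standard error do not change. The main effect only partly corrects the week-48 level contrast. Parent arm by visit terms remove the shift from both. If change from baseline is itself the response, the main effect is enough. SAP 5.2 does not say which form is meant.

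**The case against.** The strongest objection is that the premise is missing. The documents say that stopping denosumab brings rebound; they do not say that rebound grows or shrinks with duration. All entrants also had the same 96 weeks of open-label treatment immediately before entry and differ only in the year before that. Being fixed and known at baseline is equally true of age, sex or baseline CTX-I, so it is no reason by itself to choose this covariate. This stands, and it is why every effect size above is an assumption. What favours this factor is narrower: it is the one difference in exposure to the withdrawn drug that the design itself creates.

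A reader might infer that the 24 v 48 week comparison is biased. The documents do not support that. Randomisation leaves the estimate unbiased, and the ordinary standard error already allows for chance imbalance. The shifts above are conditional on an uneven split, and with K = 20 the split is 11 v 9 or better about 66% of the time (100 − 34.3).

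A reader might also infer that the SAP rules out adjustment. It is only silent: no model terms are listed at all, and the planned summary of disease-specific characteristics could include treatment history.

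Finally, the protocol's primary endpoint is a count of patients in range. Fisher's exact test on those counts is untouched by a mixed-model covariate. That too stands.

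**Conclusion.** The gap is real and minor. Entrants have two nominal durations of prior denosumab, 1.5-fold apart, and neither the allocation nor the listed analyses use this. No systematic bias follows. The benefit is modest precision and protection against an uneven draw: a 34% chance of 12 v 8 or worse under an assumed 20/20 parent split (19% to 34% over the other splits considered), a shift of 0.06 to 0.16 SD if that split occurs and exposure is worth 0.3 to 0.8 SD, and a power gain of about 1 to 3 points for effects of 0.25 to 0.5 SD. Only effects of 0.8 to 1.0 SD would bring 7 to 10 points. All of this rests on an assumed parent-arm mix and assumed exposure effects. That exposure length drives rebound is a tempting reading that the documents neither state nor support with data.

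**What to change.** In SAP 5.2 and 5.3, list the terms of the mixed models for CTX-I, P1NP and BMD, and pre-specify parent-trial arm and its interaction with visit as fixed effects. If change from baseline is the response, parent-trial arm as a covariate is enough. In SAP 5.1, add parent-trial arm by treatment group to the baseline table. In SAP 5.3, show the in-range counts by parent-trial arm descriptively and leave Fisher's exact test as it is.

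The cost is a few degrees of freedom. For the markers, with four visits, it is one main effect plus three interaction terms; for BMD, with three visits, one plus two. The data are already held from the parent trial. Stratified allocation was possible only before enrolment, and SAP section 6 places the last visit in March 2022, so it is not proposed. If the database has already been locked, the adjusted models should be reported as a labelled sensitivity analysis.
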